8.4 Protocol Deviations

The list of protocol deviations will be compiled prior to database lock. All deviations will be reviewed and decisions for handling each of the deviations will be made prior to the start of data analysis.

8.5 Endpoints

8.5.1. Primary Endpoint

FitRight® System alert value of pass (=1) or fail (=0), for each given value of fluid added (90, 150, 120, and 120 mL) and for each rotational position in the brief (sitting, laying supine, left side, and right side)

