After five minutes, staff records whether an alert was triggered. Participant will remove brief ^d		X	
All participants will complete steps above. Only the first 22 participant will go on to complete the following steps.			

Participant applies new brief (study staff checks for correct application) and participant is in sitting position. ^a		X	
Study staff pours 360 mL saline into the brief and starts a timer for ten minutes. ^b		X	
After ten minutes, participant removes brief and gives it to the staff. ^c		X	
Staff weighs out at least 10.0 grams filter paper and records the weight. Staff places the filter paper centered on the wet brief and over the acquisition and dryness layer (ADL) places the calibrated weight on the filter paper and starts a timer for one minute.		X	
After one-minute, calibrated weight and filter paper is removed and the filter paper is weighed, and the weight is recorded.		X	
Study staff will complete steps below for all participants.			
Evaluation for adverse events	X	X	X
Participant dismissal			X
^a Study activity will occur after informed consent has been signed and the participant has met all the inclusion criteria and none of the exclusion criteria.			
^b This pour will only occur if the previous pour(s) did not trigger an alert. If the previous pour did trigger an alert the participant will either move to the application of the next brief or the participant will be dismissed if they are at the end of their participation.			
^c If the Pod alerts prior to the fourth pour, it is considered a pass. If it doesn't alert after five minutes post the third pour, it is a failure. Note: There is no minimum pour volume for the first alert.			
^d Whether there was an alert triggered or not, participant will either move to the application of the next brief or the participant will be dismissed if they are at the end of their participation.			
^e This step is part of the rewet testing. Only the first 22 participants enrolled in the study will perform the rewet testing.			

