3 OBJECTIVES AND ENDPOINTS

OBJECTIVES	ENDPOINTS	JUSTIFICATION FOR ENDPOINT(S)

Primary Objective: To evaluate the FitRight® System sensor's ability to detect when an adult brief has absorbed enough liquid (~90-360 mL) normal saline via a simulated urinary void to trigger an alert to change the brief in the sitting, supine, and right or left side positions.
	
Primary Endpoint: The number of FitRight® System alerts when 90-360 mL normal saline has been absorbed into the brief in the sitting, supine, and right or left side positions.
	To determine the wetness/absorbency efficacy of the FitRight® Alert indicator in three positions

Secondary Objective: To determine the brief's residual volume capacity . In a subset of 22 participants, evaluate the FitRight® Brief after the brief has absorbed the maximum amount of liquid normal saline via a simulated
	
Secondary Endpoint: The weight of the filter paper after performing the rewet test with the FitRight® Brief after absorbing 360 mL of normal saline via a simulated void.
	To determine the brief's residual volume capacity for possible improvements to the FitRight® System.

OBJECTIVES	ENDPOINTS	JUSTIFICATION FOR ENDPOINT(S)
urinary void (360 mL) in the sitting position and then weighed via the rewet procedure.		

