After five minutes, study staff will record whether the FitRight® Alert Indicator triggered an alert. If the alert does trigger, participant will remove the brief and apply the next brief for the next position. If the alert did not trigger, study staff will apply 120mL normal saline (fourth pour) and will start a timer for five minutes. After five minutes, study staff will record whether the FitRight® Alert Indicator triggered an alert. Whether the FitRight® Alert Indicator triggered an alert or not, the participant will remove the brief and apply the next brief for the next position. Study staff will record whether the brief passed or failed to indicate. If the brief triggered an alert within the five minutes after the first, second, or third saline pour and prior to the fourth pour, the brief passed. If the brief did not trigger an alert by five minutes after the third pour, the brief fails. The fourth pour, if required, will help to determine if more volume was needed to trigger the alert or if the brief was defective.

The first 22 participants enrolled in the study will perform the rewet procedures. Participants will apply the sized brief and study staff will confirm correct application. Tubing will be setup in order to apply normal saline directly to the center of the brief. Study staff will pour 360 mL normal saline to the brief via the tubing and will start a timer for ten minutes. After ten minutes, participants will remove the brief and give the brief to the study staff. Study staff will weigh out at least 10.0 grams(g) filter paper (and as close to 10.0g as possible) and record the weight. Study staff will apply the filter paper centered on the wet brief and over the ADL layer, , apply a calibrated weight to the top of the filter paper, and start a timer for one minute. After one minute, the study staff will remove the calibrated weight and filter paper and weigh the wetted filter paper and record the weight. If any leakage or fluid infusion related issues occur during rewet testing this will be considered an invalid test (test failure) and this case will not be counted toward the 22 cases needed for rewet testing The data will still be recorded.

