6.4.2 Normal Saline Pours

Once the FitRight® System and tubing is properly setup on the participant, the study staff will pour 90 milliliters (mL) of normal saline (first pour) through the funnel system to enter the brief. Study staff will immediately start a calibrated timer for five minutes once the saline drains from the funnel system. After the five minutes, study staff will document whether the brief did or did not trigger an alert. If the brief triggers an alert, the brief passes and the participant is ready for the next brief. If the brief does not trigger an alert, study staff will pour an additional 150mL normal saline (second pour) through the funnel system and will immediately start a calibrated timer for five minutes once the saline drains from the funnel system.

After the five minutes, study staff will document whether the brief did or did not trigger an alert. If the brief triggers an alert, the brief passes and the participant is ready for the next brief. If the brief does not trigger an alert, study staff will pour an additional 120mL normal saline (third pour) through the filtration system and will immediately start a calibrated timer for five minutes once the saline drains from the funnel system.

After the five minutes, study staff will document whether the brief did or did not trigger an alert. If the brief triggers an alert, the brief passes and the participant is ready for the next brief. If the brief does not trigger an alert, the brief fails, and study staff will pour an additional 120mL normal saline (fourth pour) through the funnel system and will immediately start a calibrated timer for five minutes once the saline drains from the funnel system. After the five minutes, study staff will document whether the brief did or did not trigger an alert. No matter if the brief did or did not trigger an alert, the participant will move onto the next brief. The fourth pour, if required, will help to determine if more volume was needed to trigger the alert or if the system was defective.

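### Section 8.5.1, read literally, scores pass or fail at each of four pours, while the protocol's own rule gives one result per brief by the third pour; the fluid analyses do not estimate an effect of volume

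*Combined protocol and SAP*

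**What the plan says.** **The brief rule.** Section 4.1: "If the brief did not trigger an alert by five minutes after the third pour, the brief fails". It also names what staff record: "Study staff will record whether the brief passed or failed to indicate". Section 6.4.2 agrees: "If the brief does not trigger an alert, the brief fails, and study staff will pour an additional 120mL normal saline (fourth pour". So does footnote c of the schedule (1.2): "If the Pod alerts prior to the fourth pour, it is considered a pass". Section 4.1 gives the last pour a diagnostic purpose: "The fourth pour, if required, will help to determine if more volume was needed to trigger the alert or if the brief was defective". The endpoint in section 3 stops at the third pour's cumulative volume: "The number of FitRight® System alerts when 90-360 mL normal saline has been absorbed into the brief".

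**The stopping rule.** Footnote b, attached to pours 2 to 4: "This pour will only occur if the previous pour(s) did not trigger an alert".

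**The analysis sections.** Section 8.5.1 scores "FitRight® System alert value of pass (=1) or fail (=0), for each given value of fluid added (90, 150, 120, and 120 mL" and by position. Section 8.5.3 stratifies the pass and fail percentages by volume and position. Section 8.6 codes volume by increment, with 120 mL appearing twice. Section 8.7 sets its comparator to 1 whenever at least 90 mL was added. Section 8.9.1 plans KR-20 (full sample, by position, by fluid amount, and by both), a chi-square of fluid added against pass/fail, and Spearman correlations that include fluid volume. It speaks of three fluid amounts in one sentence and lists four in another.

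**The concern.** The primary endpoint has two scorings that do not agree. Under the brief rule, a brief that alerts after pour 3 is one pass. Scored by pour, it is two fails and a pass. A brief that first alerts after pour 4 has failed under 4.1, yet could be entered as 1 in the fourth position of 8.5.1. Section 8.9 makes the percentage of tests passed its key variable, so the unit decides what the headline number means.

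The fluid analyses raise a second problem. Later pours exist only for briefs that stayed silent, and volume is labelled by increment although the brief holds the running total. A table of pass/fail by fluid amount may then reflect the stopping rule rather than how well the sensor detects a given volume.

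**Working it through.** **Inputs from the documents.** Pours of 90, 150, 120 and 120 mL (4.1, 8.5.1). Planning pass rates of 0.85, 0.90 and 0.95, and N = 56 (8.1). Side allocation of 28 left and 28 right (8.2). Briefs: 56 + 56 + 28 + 28 = 168. Cumulative volumes: 90; 90 + 150 = 240; 240 + 120 = 360; 360 + 120 = 480 mL. The endpoint range in section 3 therefore ends at pour 3.

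**The plan's own figure.** Section 8.1 bases N = 56 on the width of a 95% interval for one proportion but states no target width, so 56 can be neither confirmed nor refuted. At 0.90 with n = 56 the exact interval is about 0.790 to 0.964. One proportion near 0.90 on 56 people fits one brief result per participant per position, not a count of pours.

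**Step 1: per-pour percentage, with an alert scored as a pass.** Let c1 to c4 be the cumulative proportions of briefs alerted by each pour, with c3 the brief pass rate.

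Per-pour percentage = c4 / [1 + (1 − c1) + (1 − c2) + (1 − c3)]

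Assume that half of the briefs silent after pour 3 alert at pour 4, so c4 = (1 + c3)/2. The low end has every passing brief alert at pour 3 (c1 = c2 = 0); the high end has every one alert at pour 1 (c1 = c2 = c3).

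| Brief pass rate | Low | High |
|---|---|---|
| 0.85 | 0.925/3.15 = 29% | 0.925/1.45 = 64% |
| 0.90 | 0.95/3.10 = 31% | 0.95/1.30 = 73% |
| 0.95 | 0.975/3.05 = 32% | 0.975/1.15 = 85% |

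If the fourth-pour assumption runs from no alerts to all alerts, the overall range is 27 to 87%.

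**Step 2: fluid table, one row per brief, by last pour given.** Every brief that ends at pour 1, 2 or 3 has passed, and every brief given pour 4 has failed. With four pours kept distinct, pass/fail is fully determined by the row, so chi-square equals n whenever there is at least one pass and one fail. Example with 151 passes and 17 fails: rows 84/0, 50/0, 17/0, 0/17 give 168.0; rows 10/0, 10/0, 131/0, 0/17 also give 168.0. If the two 120 mL pours share one label, pour 3 passes are mixed with briefs that had already failed. In the first example the merged row is 17/17, a 50% pass rate that describes neither pour.

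**Step 3: fluid table, one row per pour.** Each level gives the alert rate among briefs still silent. Illustration (assumed): 5% of briefs never alert and the rest alert with probability 0.7 at each pour, so c3 = 0.95 × (1 − 0.3³) = 0.924.

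| Pour | Rate among silent briefs | Cumulative detection |
|---|---|---|
| 1 | 66.5% | 66.5% |
| 2 | 59.6% | 86.4% |
| 3 | 44.2% | 92.4% |
| 4 | 23.7% | 94.2% |

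The per-pour rate falls while detection rises. In simulations of 168 briefs at probability 0.7, the per-pour chi-square rejects in 5, 32, 83 and 99.6% of trials when 0, 2, 5 or 10% of briefs never alert. At probability 0.5 the figures are 5, 7, 16 and 42%; at 0.9 they are 7, 95, 99.9 and 100%. These settings are illustrative: six of the twelve imply brief pass rates outside 0.85 to 0.95.

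**Step 4: comparator.** The smallest pour is 90 mL, so the 8.7 variable is 1 for every record. Pairing the result (pass rate p, q = 1 − p) with that constant gives KR-20 = 2 × [1 − (pq + 0)/pq] = 0 for any p strictly between 0 and 1.

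**The case against.** The strongest reply is that the documents already lean towards the brief. Section 8.1 counts three brief tests per participant, staff record pass or fail by brief, and 8.9 asks for the key percentage for the full sample and by position, not by pour. A reader might infer from 8.5.1 that the headline percentage will be computed per pour; the text does not establish that. Section 8.5.1 also says pass or fail rather than alert or no alert, so its fourth entry could be 0 by rule. This stands, and it makes the matter one of alignment. It does not remove the literal wording of 8.5.1.

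A reader might also infer that the fluid analyses cannot be interpreted at all. That goes too far. Alerts divided by pours given is a readable conditional rate, and when that rate is constant the chi-square rejects in about 5 to 7% of simulated trials, so repeated rows from one brief do not by themselves invalidate it. Rejections when some briefs never alert reflect a rate that truly falls. What fails is reading that rate as an effect of volume.

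Nor can one argue that the merged-label test ignores volume because its p-value changes with how passes are spread over pours 1 to 3. When briefs alert is itself detection by volume. Finally, the one-row-per-brief layout is a possible reading; 8.9.1 does not state its unit.

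The plan sets no pass-rate threshold for success, and the chi-square is an additional, exploratory analysis. That limits the stakes.

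**Conclusion.** The conflict is in the text and should be fixed before analysis. Section 8.5.1, taken literally, does not match the brief rule in 4.1, 6.4.2 and footnote c, and the rest of the plan favours the brief. Should per-pour scoring be used with an alert counted as a pass, the percentage at a 0.90 brief pass rate would be about 31 to 73%. The gap narrows when nearly all briefs alert at pour 1: at 0.95 the upper end is 85%. These are ranges under stated assumptions, not predictions.

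The fluid analyses do not estimate the effect of volume on detection. By brief with four distinct pours, chi-square is fixed at 168 by rule; by pour, it compares conditional rates in successively selected briefs. The zero KR-20 follows if the two items are the test result and the 8.7 variable, which is the comparison 8.9.1 describes. The raw data are not affected, because each pour's result is recorded.

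**What to change.** - **8.5.1 and 8.5.3:** define one outcome per brief by the protocol's own rule (1 if it alerts by five minutes after the third pour, otherwise 0), with briefs tested as the denominator. Report fourth-pour alerts descriptively, as failures.
- **8.6:** record cumulative volume at first alert (90, 240, 360, 480 mL, or none). Reconcile the three fluid amounts with the four listed in 8.9.1.
- **8.9.1, fluid:** replace the fluid chi-square and fluid Spearman term, together with the volume-stratified percentages of 8.5.3, by the cumulative proportion alerted by 90, 240 and 360 mL in each position (56 sitting, 56 supine, 28 left, 28 right), with exact 95% intervals. For scale, 50/56 = 89.3% (78.1 to 96.0) and 25/28 = 89.3% (71.8 to 97.7). Each participant gives one brief per position, so these need no clustering adjustment. Label any per-pour rate as conditional on earlier silence.
- **8.7 and KR-20:** drop the comparator and every KR-20 analysis that uses it (full sample, by position, by fluid). Make the brief pass proportion with its interval the primary result.
- **Pooled percentage over 168 briefs:** give an interval that allows for three briefs per participant, for example a bootstrap that resamples participants. With within-participant correlation ρ the design effect is 1 + 2ρ; at an assumed ρ of 0.1 to 0.5, 168 briefs carry the information of 140 down to 84.

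The cost is SAP wording in 8.5.1, 8.5.3, 8.6, 8.7 and 8.9.1. No new data are needed and no test procedure changes.

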8.5.2. Secondary Endpoint

The weight of the filter paper (in grams) after performing the rewet test with the FitRight® Brief after absorbing 360 mL of normal saline via a simulated void.

8.5.3 Additional Endpoints

The percentage of pass alerts that were correctly triggered ((# passed/tests) x 100) and the percentage of failed alerts ((# fail/ # tests) x 100) will also be evaluated for the whole sample and stratified by volume of fluid and rotational position.

8.6 Demographics, Variables and Covariates

Age will be collected as a continuous measure, with all participants being ≥ 18 years of age. Age strata will be defined as stratum 1: 18-25 years old, stratum 2: 26-41 years old, stratum 3:

42-57 years old, stratum 4: 58-67 years old, stratum 5: 68-76 years old, stratum 6: 77-94 years old, 95+ years old. Age will be considered for secondary analysis.

Sex will be collected as a categorical equal to 0=male, 1=female, 2=other, or 3=decline to answer. Sex will be considered for secondary analysis.

Brief size will be recorded as a categorical measure and will be used as a proxy for participant weight for secondary analysis.

Rotational position of the participant during the procedure will be collected as a categorical measure equal to 1=sitting, 2=supine, 3=left side or 4=right side. Rotational position will be used in the primary analysis.

Volume of simulated urine added to the brief will be collected as a categorical measure of 90 mL, 150 mL, 120 mL, and 120 mL. The volume of fluid will be used in the primary analysis.

Nominal measures of data collected will include the participant ID, date of first brief application through removal.

8.7 Derived Variables

A variable will be created to indicate if a test should have passed for a given volume of fluid added to the brief. Correct pass=1 if a minimum of 90mL of fluid, else correct pass=0.

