8.8 Handling of Missing Values

Listwise deletion of observations with missing data is necessary to correctly calculate Cronbach's coefficient alpha and for the chi-square test, therefore listwise deletion will be used for the reliability analysis and chi-square analysis. All missing data will be quantified in the final report and possible biases for any missing data will be reported.

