8.9.1 Analysis of Primary Endpoints

The primary goal of this research study is to assess the reliability of the FitRight® Alert Indicator for the full sample and stratified by the four rotational positions, the three different fluid amounts,

and the combination of rotational positions and fluid amounts. Cronbach's coefficient alpha estimate's reliability by determining the internal consistency of a test or the average correlation of items within a test. The pass/fail values from this set of test runs will be compared to the derived variable of whether or not the test should have triggered an alert. Since the variables of interest are dichotomous (pass/fail), the coefficient alpha is equivalent to the Kuder-Richardson 20 (KR-20) reliability measure. It produces a correlation measure between 0 where a high KR20 coefficient (e.g., >0.90) is indicative of a homogeneous test. A reliability of 0.70 or higher for an acceptable rating and 0.80 or higher for a good rating.

In addition, a chi-square analysis will be conducted to determine if any association between rotational position and test status (pass/fail) exists. This analysis will be repeated to examine any possible associations between fluid added and test status (pass/fail).

Spearman correlation analysis will be used to examine possible associations between the key variables of triggered alert value (pass/fail), rotational position (sitting, supine, left side, right side), and fluid volume of 90 mL, 150 mL, 120 mL, and 120 mL with covariates of age, sex, and brief size. Additional t-tests or non-parametric tests will be employed to further examine any significant associations found in the correlational analyses between key and covariate measures.

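### KR-20 in section 8.9.1 has no defined items; against the constant 8.7 variable it is 0 or undefined, and no other item set makes it a measure of detection

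*Combined protocol and SAP*

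**What the plan says.** All references are to the combined protocol and SAP.

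- **Statistic (8.9.1).** The primary goal is the reliability of the alert indicator. The statistic is coefficient alpha, which the section equates with KR-20 for pass/fail data and describes as reflecting "the internal consistency of a test or the average correlation of items within a test". The rating is "A reliability of 0.70 or higher for an acceptable rating and 0.80 or higher for a good rating".
- **Comparison (8.9.1).** "The pass/fail values from this set of test runs will be compared to the derived variable" of whether an alert was due. No list of items is given, and nothing says what forms a row.
- **Comparator (8.7).** "Correct pass=1 if a minimum of 90mL of fluid, else correct pass=0".
- **Volumes (8.6).** Volume is "collected as a categorical measure of 90 mL, 150 mL, 120 mL, and 120 mL". Sections 4.1 and 6.4.2 give the same pours, and neither plans a dry or smaller test.
- **Breakdown (8.9.1).** Reliability is to be "stratified by the four rotational positions, the three different fluid amounts", and also by "the combination of rotational positions and fluid amounts".
- **Missing values (8.8).** "Listwise deletion of observations with missing data is necessary to correctly calculate" the coefficient.
- **Design facts.** A later pour is given only if earlier pours produced no alert (1.2, footnote b). A brief fails if it has not alerted by five minutes after the third pour (4.1). Each person lies on one side only, 28 right and 28 left (8.2).
- **Pass percentages.** These are planned in 8.5.3 and 8.9, and 8.1 bases N=56 on a 95% CI for the proportion of successful alerts.

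**The concern.** KR-20 measures how items vary together across rows, so it needs named items that vary. Section 8.9.1 names none, and the one comparator it offers cannot vary under this design. Followed literally, the analysis returns zero or no value whatever the sensor does.

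Two things are at stake. First, the coefficient carries quality labels and stands first in the primary endpoint analysis, so readers will tend to take it as a verdict on detection. Second, with the items left open, the analyst must choose an item set after the data are in, and the coefficient depends heavily on that choice.

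**Working it through.** **The plan's own figures.** The documents give no expected KR-20, only the two thresholds, so there is no coefficient to reproduce. For N=56 the full 95% CI widths at pass rates 0.85, 0.90 and 0.95 are 0.187, 0.157 and 0.114 (Wald) or 0.202, 0.174 and 0.134 (Clopper-Pearson). Section 8.1 states no target width, so N=56 can be neither confirmed nor refuted from it.

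**Formula.** For k pass/fail items with pass proportions p_i and q_i = 1 - p_i, and T the row total:

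KR-20 = k/(k-1) × [1 - Σ p_i q_i / Var(T)]

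**1. Alert against the 8.7 variable (k=2).** Pours are 90, 150, 120 and 120 mL, or 90, 240, 360 and 480 mL cumulatively. All are at least 90, so the 8.7 variable is 1 in every row and its variance is 0. Hence Σ p_i q_i = pq and Var(T) = pq, giving KR-20 = 2 × (1 - pq/pq) = 0. With 50 of 56 passing, pq = 0.0957 and KR-20 = 2 × (1 - 0.0957/0.0957) = 0. If all pass or all fail, the ratio is 0/0. This was checked for every failure count from 1 to n-1 at n = 28, 56 and 168, and needs no assumed pass rate.

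**2. Three positions as items (k=3, 56 rows).** Take six failures in each position, so 150 of 168 briefs pass (89.3%). Then p_i q_i = (50/56)(6/56) = 0.0957 and the sum is 0.2870.

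| Pattern of failures | Pass rate | Var(T) | KR-20 |
|---|---|---|---|
| Six people fail all three | 89.3% | 9 × 0.0957 = 0.8610 | 1.5 × (1 - 0.2870/0.8610) = 1.00 |
| 18 people fail one each | 89.3% | (18/56)(38/56) = 0.2181 | 1.5 × (1 - 0.2870/0.2181) = -0.47 |
| 50 people fail all three | 10.7% | 0.8610 | 1.00 |
| Nobody fails | 100% | 0 | undefined |

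The coefficient follows how failures cluster within people, not how many there are. Adding the constant 8.7 variable as a fourth item changes k/(k-1) from 3/2 to 4/3, which multiplies each defined value by 8/9.

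**3. Four positions as items.** Nobody has both left and right, so listwise deletion leaves no rows.

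**4. Pours as items.** A brief that alerts has no later pours, so listwise deletion removes the briefs that alerted early. With four pours, only briefs that fail under 4.1 remain. With three, only briefs without an alert after pour two remain. In both cases every earlier pour is a constant fail, so KR-20 is 0 or undefined.

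**5. Position-by-fluid cells.** In a 90 mL or 150 mL cell each person gives at most one alert value. KR-20 then has either one item (k/(k-1) is undefined) or the alert plus the constant (0 or undefined, as in step 1).

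**The case against.** Four arguments weigh against the point.

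*Position and fluid amount are named as strata, not items.* This is fair. The only comparison the text describes is the one in step 1, and the point rests on it. Steps 2 to 5 show only that a different choice of items would not repair the analysis.

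*The plan rates reliability, and nowhere claims that KR-20 measures detection.* This is also fair, and that alpha is not a pass rate is true of alpha in general. But it does not answer the defects specific to this plan: undefined items and a constant comparator.

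*Detection is already covered.* Largely so. Section 8.9 treats the pass and fail percentages as the key variable, and 8.5.3 breaks them down by volume and position. However, the promise of confidence intervals in 8.9 is for means; no interval method is named for the pass proportion.

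*Nothing hinges on the coefficient.* Correct. The documents attach no success criterion to it.

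Three stronger readings are tempting but unsupported:

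- A reader might infer that the study cannot estimate detection. It can: every brief's alert is recorded and the percentages are planned.
- A reader might combine position-based alphas with pour-based alphas in which an alert is carried forward, and quote a spread from about -0.02 to 0.95 at 90% pass. That joins two different statistics, and the plan has no carry-forward rule. For positions alone at 90% pass, simulated medians run from -0.02 to 0.74 as an assumed within-person correlation goes from 0 to 0.5.
- A reader might say N=56 was sized on the per-position proportion. Section 8.1 names only the proportion of successful alerts and says nothing about per position.

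**Conclusion.** The point holds and should be fixed before analysis. As written, the one comparison described in 8.9.1 yields KR-20 = 0, or no value when all briefs pass or all fail. That is algebra from the planned volumes and rests on no assumption about performance. No item set that the design can supply turns the 0.70 and 0.80 ratings into a statement about detection: 10.7% detection can score 1.00, 89.3% can score 1.00 or -0.47, and a sensor that alerts in every brief at 90 mL gets no coefficient at all. The failure patterns in step 2 are illustrations, not predictions.

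The consequence is limited to the coefficient and its label. No data are lost and no decision in the documents turns on it.

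**What to change.** **Remove** KR-20, its rating thresholds and the 8.7 variable from the primary analysis.

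**Make primary** the proportion of briefs passing under the 4.1 rule (alert by five minutes after the third pour), with an exact (Clopper-Pearson) 95% CI for each of sitting, supine and side-lying. Each has n=56; 50/56 gives 0.78 to 0.96. Name the 4.1 rule explicitly, because 8.5.1 codes pass and fail for each pour. This is the type of interval named in 8.1.

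**Show left and right descriptively** with exact CIs, n=28 each; 25/28 gives 0.72 to 0.98.

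**If a pooled 168-brief figure is reported,** make it secondary, with one pre-specified interval that allows for three briefs per person. One conservative option applies the Clopper-Pearson formula at an effective n of 56, with passes divided by 3. Other methods would also serve. The size of the choice at 151/168, using effective n = 168/(1 + 2r) for an assumed within-person correlation r (the documents give none):

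| r | Effective n | Clopper-Pearson half-width |
|---|---|---|
| 0 (independent) | 168 | 0.049 |
| 0.1 | 140 | 0.053 |
| 0.3 | 105 | 0.062 |
| 0.5 | 84 | 0.070 |
| 1 (the n=56 rule) | 56 | 0.087 |

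**Cost.** SAP wording only, with no new data, procedure or CRF field. A pooled interval, if reported, becomes wider than one that treats briefs as independent, by the amounts in the table.
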